3. ***Our study will be first to explore the relationship of C4 copy number variation to cardiometabolic risk in African-American adults or adolescents.*** The effects of C4 gene copy number variation of longevity have varied among different ethnic groups. As indicated below, we have found increased C4L gene copy number is associated with impaired endothelial function in nonHispanic white adolescents. Whether this relationship is present in African-Americans is unknown.

It is important that studies be done in this age group to determine the early role of complement genetics in the development of cardiometabolic risk before the onset of overt disease or other co-morbidities and their treatment confound potential relationships. ***The results of this study will help us gain a full understanding of the role of complement in increasing cardiovascular risk in African-Americans and in potentially developing genetic methods of identifying at-risk individuals.***

PRELIMINARY STUDIES

Demographics: Thirty-four of the 75 subjects were female. Mean age was 15.0 ± 1.7 years and mean BMI was 22.0 ± 5.8 kg/m²) were studied.

Complement and body habitus: Robust rank order regression analysis with was used to assess relationships between C3 and C4 protein levels, C4 gene copy number variation to body habitus, lipids, inflammation, carbohydrate metabolism, and clotting factor. Age and sex were included in all models. The cut-off point for outliers was 3 and 100 iterations were performed. Results are presented as 95% confidence intervals.

C3, C4, C3a, C4a, and C5a levels did not differ between sexes and were not significantly related to age. C3 levels positively correlated with all measures of body mass and adiposity (Figure 1). The correlation with FMI ($R^2=0.41$) was better than with FFMI ($R^2=0.22$). C4 levels were not related to any measure of body habitus. For C3a, C4a and C5a the only significant relationship was between C4a and FFMI ($\beta=9.82$, CI: 1.55-18.1).

[figure not shown]

Figure 1: Relationships of C3 levels to measures of body habitus. BMI: $\beta=35.9$; CI: 23.6-48.2; BMI%: $\beta=5.22$; CI: 3.35-7.08; Waist circumference: $\beta=15.4$; CI: 10.01-20.9; Body Fat %: $\beta=18.6$; CI: 12.5-24.7; FMI: $\beta=49.2$; CI: 33.2-65.2; FFMI $\beta=52.9$; CI: 14.9-90.1.

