Increased C4S copy number was associated with increased insulin secretion ($\beta=0.29$; CI: 0.06-0.52) and decreased endothelin 1 ($\beta=-0.15$; CI: -0.30--0.01). WBC ($\beta=-0.79$; CI: -1.56--0.02) and neutrophil count ($\beta=-0.87$; CI: -1.48--0.33) both decreased with increasing C4B copy number.

Figure 2: Relationship of HDL to C4 type copy number. C4L: $\beta=3.59$; CI: 1.19-6.00; C4S: $\beta=0.4.26$; CI: -7.50—1.02; C4A: $\beta=4.33$; CI: 1.00-7.66; C4B $\beta=-5.56$; CI: -10.3--0.87.

Interestingly, the measures of inflammation, IL6 and CRP were not related to C4 copy number nor were AIX₇₅ or PAI-1.

RESEARCH DESIGN AND METHODS

All three specific aims will be studied using the same subjects and research procedures.

Subjects: One hundred Africa-American adolescents between the ages of 12 and 18 will be recruited to participate. There will be no weight or BMI criteria and we plan to recruit subjects across a wide range of BMI's. This will allow us to determine the role of C3 and C4 levels, C3 polymorphisms and C4 copy number variation in determining adolescent obesity and cardiometabolic risk. Subjects must be on no chronic medications except for contraceptives in females. Subjects will be expected to be medication free for at least 2 weeks prior to study except for contraceptives. Subjects with a history of autoimmune disease, either endocrine or connective tissue type will be excluded. Subjects with a history of hematologic or renal disease, malignancy or other chronic disease will also be excluded. Subjects with a history of asthma or attention deficit disorder will be allowed to participate as long as they meet the medication requirements.

To avoid potential racial confounders as described in the preliminary data, we plan to recruit only African-American subjects. Subjects will be recruited to specifically fill 3 different weight classes (70 % lean, BMI <85%: 10% overweight BMI<95%: 20% obese BMI>95%) for both sexes. These match the reported US prevalences for overweight and obesity.⁷⁶

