Complement genotypes: C3 genetic variants including the DNA sequence polymorphisms for G102R for fast and slow allotypes, and SNPs for rs11569562 and rs2250656 that modulate C3 plasma protein levels will be typed for all study subjects. Copy-number variations for total C4, C4A, C4B, long genes and short genes of C4 will be elucidated by Southern blot analyses of genomic DNA samples digested by Pmel, Taql, PshAI/Pvull and resolved by gel electrophoresis.⁷⁴ Samples for subjects with ambiguous data will be subject to realtime quantitative PCR using five different amplicons and the results will be validated as the gene copy-numbers in each subject for total C4=C4A+C4B=long genes+short genes.⁸⁵

Cardiovascular measures, glucose and insulin: IL6, CRP, endothelin 1, fibrinogen, PAI1 glucose and insulin will be measured in the CORE laboratory. Plasma lipids will be measured in the clinical laboratory of the Wexner Medical Center.

Data analysis: **Specific Aim 1:** To determine whether there are racial differences in complement C3 and C4 levels in healthy adolescents and how they relate to cardiometabolic risk factors including triglyceride and LDL levels, inflammation, and vascular function.

Statistical methods: Complement levels from African-Americans in this proposal will be compared to those from nonHispanic whites in our current study. Eligibility criteria are identical for both studies except for race. Data will be assessed for normality using the Shapiro Wilk test ($p>0.05$ indicative of normality). Non-normal data will be log normalized if possible. Unpaired t-tests will be used to compare differences in C3 and C4 levels as well as cardiometabolic risk factor results (reactive hyperemia, augmentation index, Matsuda index, insulin secretion, lipids, inflammatory markers, and PAI-1). We anticipate age and BMI differences will be minimal but should racial differences be found analysis of covariance will be done to account for any difference found.

Robust rank order regression analysis will be used to assess relationships between C3 and C4 protein levels to body habitus, lipids, inflammation, carbohydrate metabolism, and clotting factor in each race individually and in the group as a whole. Age and sex will be included in all models. The cut-off point for outliers was 3 and 100 iterations were performed. Results are presented as 95% confidence intervals.

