Sample size: Based on data from our previous study with 100 nonHispanic white subjects and 100 African-American subjects we have power 0.8 to detect a 15% racial difference in C4 levels and 7.5% difference in C3 levels.

Interpretation: There are two major portions of this aim. The first is to determine whether there are complement levels differences between the racial groups and the second is to determine how these affect previously demonstrated racial differences in cardiovascular risk¹². The former will be easily determined by comparing complement levels in the two groups. The hypothesis that these racial differences are responsible for at least some of the cardiometabolic racial differences will be proven if when complement levels are included in the regression equation they retain significance but the racial differences are lost. Lastly, even if racial differences in complement are not found or do not account for cardiometabolic risk differences it will still be important for us to determine whether the significant effects of complement described above in nonHispanic whites are present in African-American adolescents.

Specific Aim 2: To determine whether specific C3 polymorphisms, F versus S, A>G at rs11569562 and/or rs2250656, are associated with increased cardiometabolic risk in African-Americans.

Statistical Methods: As indicated above, the C3F gene has been associated with increased risk of myocardial infarction in several populations³⁶⁻³⁸ and Phillips et al⁴⁰ reported increased cardiometabolic risk in subjects with either an A/A or A/G versus subjects with a G/G genotype for both the rs11569562 and the rs2250656 sites. For rs11569562 in a European population ~ 25% of subjects had G/G and for rs2250656 ~10% had G/G. Frequencies in the African-American population are unknown. Data will be assessed for normality using the Shapiro Wilk test ($p>0.05$ indicative of normality). Non normal data will be log normalized if possible. Unpaired t-tests with unequal sample sizes will be used for comparisons for each of the measured normal variables between subjects with at least one A allele gene and those with two G alleles assuming the data is normally distributed. Mann-Whitney U tests will be used to assess non-normal data.

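### The Aim 1 t-test/ANCOVA race comparison of risk factors leaves out sex, although the plan's regressions for Aims 1 and 3 always include it

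*Combined protocol and SAP*

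**What the plan says.** All places are in the combined protocol and SAP.

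- **Data analysis, Specific Aim 1, Statistical methods**, on the race comparison: "Unpaired t-tests will be used to compare differences in C3 and C4 levels as well as cardiometabolic risk factor results". The risk factors listed are lipids, inflammatory markers, PAI-1, the Matsuda index, insulin secretion and two vascular measures, reactive hyperemia and augmentation index.
- **Same section**, on adjustment: "We anticipate age and BMI differences will be minimal but should racial differences be found analysis of covariance will be done". Age and BMI are the only variables named, and the adjustment depends on a difference being seen.
- **Same section**, on the regressions of these outcomes on complement levels, which are run "in each race individually and in the group as a whole. Age and sex will be included in all models". Specific Aim 3 repeats the rule on age and sex.
- **Specific Aim 1, Interpretation**: the explanatory hypothesis counts as proven if "when complement levels are included in the regression equation they retain significance but the racial differences are lost".
- **Research Design and Methods, Subjects**: "One hundred Africa-American adolescents between the ages of 12 and 18 will be recruited to participate", and "Subjects will be recruited to specifically fill 3 different weight classes". The quotas apply in both sexes, but no ratio of girls to boys is given.
- **Preliminary Studies, Demographics**, on the white cohort: "Thirty-four of the 75 subjects were female".

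**The concern.** The comparison is not randomised. White adolescents from an ongoing study are set against African-American adolescents recruited later, through separate advertising. Eligibility is the same apart from race, but that does not fix the sex mix. The weight-class quotas control BMI category within each sex and leave the proportion of girls free.

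If the cohorts differ in that proportion, and a risk factor differs between girls and boys, part of the sex difference will be reported as a race difference. The plan treats sex as a standing covariate in its Aim 1 and Aim 3 regressions, yet omits it from the step that contrasts two cohorts directly.

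There is a second, smaller issue. The Interpretation paragraph looks for a race effect that disappears when complement is added, but it does not say which model supplies the race effect beforehand. If that effect came from the t-test, and the later one from a regression with age and sex, the effect could disappear because sex was added and not because complement was.

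**Working it through.** **1. The plan's own figure.** The Aim 1 sample-size paragraph claims power 0.8 with 100 per group for a 15% difference in C4 and 7.5% in C3. It gives no mean, SD or alpha, so it cannot be reproduced directly. With two-sided alpha 0.05 (assumed), the detectable standardised difference is (1.960 + 0.842) × √(2/100) = 0.396 SD. The stated percentages then imply coefficients of variation of 0.15/0.396 = 37.9% for C4 and 0.075/0.396 = 18.9% for C3. The 0.396 SD serves below only as a yardstick.

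**2. Inputs for the bias.**
- Female share of white subjects: w = 34/75 = 0.453. This describes the 75 preliminary subjects; the mix of the planned 100 is not given.
- Female share of African-American subjects: p, not given, so varied.
- Sex difference in a risk factor: D, in within-sex SDs. The documents report none, so 0.3, 0.5 and 0.8 are assumed.
- Group sizes 100 and 100, no true race difference, nominal two-sided 5%.

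**3. Formulas.**
- Bias = (p − w) × D
- SE = √{[1 + D²p(1−p)]/100 + [1 + D²w(1−w)]/100}
- Type I error = Φ(−1.96 + bias/SE) + Φ(−1.96 − bias/SE)

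Example, 20 points and D = 0.8 (p = 0.653): bias = 0.20 × 0.8 = 0.160. SE = √[(1.145 + 1.159)/100] = 0.152. Ratio = 1.054. Type I error = Φ(−0.906) + Φ(−3.014) = 0.184.

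**4. Results** (bias in SD; type I error)

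| African-American female share | D = 0.3 | D = 0.5 | D = 0.8 |
|---|---|---|---|
| 45.3% (matched) | 0; 5.0% | 0; 5.0% | 0; 5.0% |
| 50% (4.7 points) | 0.014; 5.1% | 0.023; 5.3% | 0.037; 5.7% |
| 55.3% (10 points) | 0.030; 5.5% | 0.050; 6.4% | 0.080; 8.2% |
| 65.3% (20 points) | 0.060; 7.0% | 0.100; 10.6% | 0.160; 18.4% |

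The largest bias shown, 0.160 SD, is 0.160/0.396 = 40% of the detectable difference. At a 50% female share the bias is at most 0.037/0.396 = 9% of it.

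**5. Precision when sex is balanced.** The share of variance due to sex is s = (D²/4)/(1 + D²/4), which is 2.2%, 5.9% and 13.8% for the three values of D. For a difference with 80% power unadjusted, adjusted power is Φ(2.802/√(1−s) − 1.960) = 0.809, 0.823 and 0.855.

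**6. C3 and C4.** Preliminary Studies reports that neither level differed between the sexes. With D near zero, the bias is near zero whatever p is.

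**The case against.** A reader might infer that the plan never adjusts a race effect for sex. The documents do not support that. The Aim 1 regressions include a pooled model with age and sex, and the Interpretation criterion implies a race term in such a regression. That criterion also refers to racial differences shown previously, so the plan does not say that the t-test results feed it.

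This limits the point to the t-test/ANCOVA step, but does not remove it. The race term is implied and not written into the model. The regression outcomes listed under Aim 1 do not name vascular function. It may be intended, since the preliminary section has a similar list and its Table 1 includes reactive hyperemia and augmentation index. As written, though, the t-test/ANCOVA is the only race comparison spelled out for those two measures.

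A second objection is that a large imbalance is not to be expected, and this has force. If both groups were random samples with 45.3% girls, the SE of the difference in female share would be √(0.453 × 0.547 × 2/100) = 0.070. A gap of 15 points (2.13 SE) would then arise about 3% of the time, and one of 20 points (2.84 SE) less than 1%. Recruitment by advertisement is not random sampling, so this is only a benchmark, but nothing in the documents points to a skew of that size.

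Third, Aim 1 is sized only for C3 and C4, where no sex difference was seen. That stands: the concern applies to the risk factors.

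**Conclusion.** The point holds for the Aim 1 t-test/ANCOVA comparison of risk factors. The inconsistency with the plan's regressions is certain; its effect is conditional. There is no bias if the sex mix matches, a negligible one near a 50% female share (type I error about 5-6%), and a modest one at 10 points (about 5-8%). The figure of about 18% needs a 20-point imbalance together with a 0.8 SD sex effect. Neither is documented, so it is an outer limit and not an expected error rate.

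A reader might also infer that the C3 and C4 comparisons are compromised, or that the African-American sample should be recruited to 45% female. The first conflicts with the preliminary finding of no sex difference. The second rests on a share known only for 75 of the planned 100 white subjects, and is unnecessary once sex is in the model. The case for change rests on consistency, protection against an unknown imbalance, and some gain in precision where sex affects the outcome.

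**What to change.** In the Aim 1 statistical methods, replace the t-test with conditional ANCOVA by one rule: each race difference in a risk factor, and in C3 and C4 for uniformity, is estimated from a linear model with race, sex and age always included, whether or not an imbalance is observed.

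In the Aim 1 Interpretation, write out the race term and state that the models with and without complement share these base covariates. A race effect that disappears can then not be due to the addition of sex.

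The cost is about one sentence in each place and two degrees of freedom for sex and age. The pooled regression already needs both variables in both cohorts, so no new data, visits or recruitment target are required.

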Complement and cardiometabolic risk: C3 and C4 levels were significantly related to several cardiometabolic risk factors (Table 1). Regarding vascular function, the percent fall in FVR following upper arm arterial occlusion decreased as both C3 and C4 increased. This decrease in reactive hyperemia indicates worsening endothelial function. Alx₇₅ was not significantly related to either C3 or C4. Increased inflammation correlated primarily with increased C4 levels as indicated by significant relationships to white blood cell and neutrophil counts as well as IL6. White blood cell and neutrophil count also positively correlated with C3 levels. LDL and triglyceride levels positively correlated with C3 levels while HDL negatively correlated with both C3 and C4 levels. Insulin secretion increased and sensitivity during OGTT decreased as C3 levels increased. Endothelin 1 and PAI1 levels were not significantly related to either C3 or C4 levels. C3a was positively related to IL6 ($\beta=0.003$; CI: 0.001-0.006). C4a was negatively related to disposition index ($\beta=-0.015$; CI: -0.028--0.002).

Many of the cardiometabolic risk factors were related to one or more of the measures of body habitus. Adjusted values were calculated based on the body habitus measure to which they were most closely related. Reactive hyperemia, neutrophil count, LDL and insulin sensitivity were adjusted for percent body fat, HDL and triglycerides for waist circumference, and insulin secretion and PAI1 for FMI. Alx₇₅, white blood cell count, IL6 endothelin 1 were not related to any measure of body habitus so no adjustments were done. Adjustment for CRP was not done since many of the levels were at the lower limit of detectability. After adjustment C3 and C4 levels continued to be significantly related to the reactive hyperemia response. C3 was not significantly related to any of the other adjusted variables while C4 remained positively related to adjusted neutrophil count and negatively related to HDL.

Complement genetics: For C3 the only significant difference was lower HDL levels in subjects with at least one F allele (46.7 ± 12.2 versus 54.1 ± 13.1 , $p=0.028$) which would indicate

Table 1: Relationship C3 and C4 to cardiometabolic risk factors in nonHispanic white adolescents.

	C3 β	C4 β
Reactive Hyperemia	0.012 (0.006-0.019)	0.028 (0.013-0.043)
Adjusted	0.007 (0.001-0.014)	0.023 (0.007-0.039)
AIX ₇₅	0.007 (-0.011-0.025)	0.044 (-0.002-0.089)

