White Blood Cell Count	0.002 (0.0002-0.005)	0.007 (0.003-0.012)
Neutrophil Count	0.002 (0.0002-0.003)	0.007 (0.004-0.011)
Adjusted	-0.0004 (-0.001-0.002)	0.005 (0.002-0.007)
CRP	0.003 (-0.001-0.006)	0.0005 (-0.001-0.002)
IL6	0.0004 (-0.00005-0.001)	0.001 (0.0002-0.002)
LDL	0.021 (0.0004-0.041)	-0.024 (-0.074-0.027)
Adjusted	0.013 (-0.007-0.033)	-0.040 (-0.087-0.007)
HDL	-0.012 (-0.023--0.001)	-0.027 (-0.054--0.0003)
Adjusted	0.002 (-0.007-0.012)	-0.026 (-0.048-0.004)
Triglycerides	0.054 (0.025-0.083)	0.055 (-0.020-0.1)
Adjusted	0.009(-0.027-0.046)	0.057 (-0.014-0.127)
Matsuda insulin sensitivity	-0.003 (-0.004--0.001)	-0.001 (-0.006-0.004)
Adjusted	0.0003 (-0.002-0.001)	0.086 (-0.004-0.176)
Insulin Secretion	0.001 (0.0004-0.002)	0.002 (0.001-0.004)
Adjusted	-0.0001 (-0.001 0.001)	0.002 (-0.00006-0.004)
Disposition Index	-0.0004 (-0.003-0.002)	0.005 (-0.001-0.011)
Endothelin-1	-0.0002 (-0.001-0.0003)	-0.001 (-0.002-0.0004)
PAI-1	0.002 (-0.0002-0.005)	0.0003 (-0.004-0.005)
Adjusted	-0.0004 (-0.002-0.002)	-0.001 (-0.005-0.004)

increased risk in subjects with one F allele. This will be important to explore in this proposal since HDL levels differ between African-Americans and Caucasians.

FFMI decreased as C4T ($\beta=-0.73$; CI: -1.24--0.22) and C4L ($\beta=-0.46$; CI: -0.81--0.10) copy number increased. C4S, C4A, and C4B copy number were not related to any measure of body habitus. C4T gene copy number was not related to any of the cardiovascular risk factors but relationships were found for the various C4 subtypes. Interestingly, HDL was significantly

related to all 4 subtypes and increased C4L copy number increased ($\beta=3.59$; CI: 1.19-6.00), decreased as C4S ($\beta=0.4.26$; CI: -7.50—1.02) and C4B ($\beta=-5.56$; CI: -10.3--0.87) increased and increased as C4A increased ($\beta=4.33$; CI: 1.00-7.66) (**Figure 2**). These relationships are particularly interesting in light of the relationship of C4 levels to HDL and suggest that C4 may play a role in determining HDL levels.

LDL and triglyceride levels were not associated with any of the C4 gene copy numbers. Interestingly, while increased C4L gene copy number was associated with increased HDL, it was also associated decreased insulin secretion ($\beta=-0.24$; CI: -0.44-0.05) and decreased disposition index ($\beta=-0.61$; CI: -1.14--0.08).

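### The Aim 1 regressions and the race rule commit to no adiposity covariate, so as written they cannot separate C3 from adiposity

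*Combined protocol and SAP*

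**What the plan says.** **The plan.** Data analysis, Specific Aim 1, Statistical methods, regresses body habitus, lipids, inflammation, carbohydrate metabolism and clotting on C3 and C4 "in each race individually and in the group as a whole. Age and sex will be included in all models". Adiposity appears there only among the regressed variables.

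The one planned BMI adjustment follows the t-tests between races. Age and BMI are expected to be similar, but "should racial differences be found analysis of covariance will be done to account for any difference found".

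Under Specific Aim 1, Interpretation, the hypothesis that complement accounts for part of the race differences in risk "will be proven if when complement levels are included in the regression equation they retain significance but the racial differences are lost". No other terms of that equation are named.

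**The preliminary data (75 white adolescents).** Complement and body habitus reports that "C3 levels positively correlated with all measures of body mass and adiposity", with R² 0.41 for fat mass index, and finds C4 unrelated to habitus. Complement and cardiometabolic risk then goes beyond age and sex: "Adjusted values were calculated based on the body habitus measure to which they were most closely related". Reactive hyperemia stayed related to C3 after this step, but "C3 was not significantly related to any of the other adjusted variables". The Aim 1 plan does not repeat the step.

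**The opening claim.** Specific Aims describes the C3–triglyceride correlation in white adolescents as independent of obesity.

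**The concern.** C3 tracks fat mass, fat mass tracks lipids and insulin resistance, and subjects are recruited over a wide BMI range. A C3 slope adjusted only for age and sex therefore mixes any effect of C3 with adiposity.

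This carries into the race rule. The part of a race difference that a regression credits to C3 is the C3 slope multiplied by the race difference in C3. If the slope carries adiposity, the credit is inflated even when the races have equal adiposity. BMI-class quotas therefore do not remove the problem. Nor does an analysis of covariance that is triggered by a race difference in BMI.

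The directions also fit. The Background reports lower C3 in African-American adults, and lower triglycerides and higher HDL in African-American adults and adolescents. Lower C3 combined with a positive triglyceride slope and a negative HDL slope would appear to explain both lipid differences. The main mechanistic conclusion of Aim 1 could then be declared on an adiposity slope.

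**Working it through.** **1. Printed C3 coefficients.** Inputs: Table 1, C3 column, for every outcome that was significant before adjustment and then habitus-adjusted. Fall = 1 − adjusted β / unadjusted β.

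| Outcome | Unadjusted β (95% CI) | Adjusted β (95% CI) | Fall | Adjusted CI includes 0 |
|---|---|---|---|---|
| Triglycerides | 0.054 (0.025 to 0.083) | 0.009 (−0.027 to 0.046) | 1 − 0.009/0.054 = 83% | yes |
| HDL | −0.012 (−0.023 to −0.001) | 0.002 (−0.007 to 0.012) | 1 + 0.002/0.012 = 117% | yes |
| LDL | 0.021 (0.0004 to 0.041) | 0.013 (−0.007 to 0.033) | 1 − 0.013/0.021 = 38% | yes |
| Reactive hyperemia | 0.012 (0.006 to 0.019) | 0.007 (0.001 to 0.014) | 42% | no |
| Neutrophils | 0.002 (0.0002 to 0.003) | −0.0004 (−0.001 to 0.002) | 120% | yes |
| Matsuda index | −0.003 (−0.004 to −0.001) | 0.0003 (−0.002 to 0.001) | 110% | yes |
| Insulin secretion | 0.001 (0.0004 to 0.002) | −0.0001 (−0.001 to 0.001) | 110% | yes |

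Six of the seven lose significance. The last three rows have coefficients of one significant digit. The adjusted neutrophil and Matsuda estimates also sit poorly in their intervals (midpoints 0.0005 and −0.0005), so their percentages are soft.

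**2. Why the printed values are not rescaled.** The documents do not say exactly how the adjustment was made. After adjustment the triglyceride interval widens from 0.058 to 0.073 (×1.26), while the HDL interval narrows from 0.022 to 0.019 (×0.86). These widths do not point to one method, so a correction that presumes one is not dependable.

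**3. Could the race rule be met with no C3 effect?** This is an illustration with assumed inputs:
- 100 against 100 subjects, equal adiposity, no direct C3 effect, normal data, least squares.
- C3–adiposity correlation 0.64 (√0.41, fat mass index) or 0.556. The second comes from the printed waist slope: SE = (20.9 − 10.01)/(2 × 1.994) = 2.73; t = 15.4/2.73 = 5.64; R² = t²/(t² + 71) = 0.309; √0.309 = 0.556.
- Adiposity-driven C3–triglyceride correlation 0.10–0.30. The unadjusted Table 1 row corresponds to about 0.40.
- Triglycerides lower by 0.3–0.6 SD in African-Americans.
- C3 lower by 0.40 SD, the difference detectable at power 0.8 (two-sided α 0.05 assumed): (1.96 + 0.84) × √(2/100) = 0.396. Also 0.20 and 0.10 SD.
- Rule met when race has p < 0.05 without C3 and, with C3 added, C3 has p < 0.05 and race p ≥ 0.05.

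| C3 gap | Rule wrongly met, no adiposity term | Adiposity in the model |
|---|---|---|
| 0.40 SD | about 1–31% | under 1% |
| 0.20 SD | about 0.2–15% | under 1% |
| 0.10 SD | about 0.3–8% | under 1% |

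The low ends below 1% rest on few simulated studies and are imprecise.

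**4. Cost in precision.** At R² 0.41 the variance inflation is 1/(1 − 0.41) = 1.69, so the C3 standard error rises by up to √1.69 = 1.30, about 30%. It rises by less where adiposity also reduces residual variance.

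**The case against.** **It may be shorthand.** The Aim 1 regression paragraph closely repeats the preliminary methods text, including a past-tense line on outliers and iterations. That text also named only age and sex, and habitus-adjusted results followed. This stands as an explanation: the sponsor may intend to adjust again. It does not cure the plan, which makes no such commitment, and the race rule, which has no counterpart in the preliminary text, names no adiposity term either.

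**Adiposity may be a mediator.** The Background reports that C3 knock-out mice resist diet-induced obesity, and the Subjects section wants to study the role of complement in obesity. If C3 acts partly through fat, adjustment removes part of its effect. This stands, and is why both models are needed.

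**The illustration depends on its inputs.** A C3 gap of 0.40 SD is the detectable difference, not an expected one, and the rates fall with smaller gaps. This stands; the range is shown. Future Directions also concedes that cross-sectional studies do not prove causation, which tempers the rule but does not change when it is met.

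**Stronger readings.** A reader might infer that C3 has no effect on triglycerides or HDL. The documents do not support that: there were 75 subjects, the adjusted intervals are wide, and the unadjusted LDL and HDL intervals only just excluded 0, so losing significance is weak evidence alone. A reader might also infer that triglycerides and HDL are the outcomes most affected. As printed, neutrophils, Matsuda index and insulin secretion all fall by more than triglycerides, so no ranking over all outcomes holds.

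**Conclusion.** The point holds and should be fixed. As written, the Aim 1 regressions cannot separate C3 from adiposity, and the race rule can credit an adiposity slope to C3.

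The evidence is the sponsor's own: fat mass index R² 0.41 with C3, and six of seven C3 associations no longer significant after adjustment. HDL and triglycerides matter here because they are the lipids reported to differ by race and their C3 coefficients fall far more than that of LDL. The size of the risk under the race rule is illustrative only, with upper ends of 31%, 15% and 8% at C3 gaps of 0.40, 0.20 and 0.10 SD. The slopes come from white adolescents; those in African-American adolescents are unknown.

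C4 is not exempt. It was unrelated to habitus in the white adolescents, but the Background reports strong BMI–C4 correlations in each race group of adults.

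The opening statement that the C3–triglyceride correlation is independent of obesity is not supported by the adjusted Table 1 row.

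**What to change.** In Specific Aim 1, Statistical methods, for each outcome that is not itself a habitus measure, report for both C3 and C4:

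- (a) complement, age and sex;
- (b) the same plus one pre-named adiposity measure, entered jointly and obtained the same way in both cohorts. BMI or waist would serve, or DEXA fat mass index if the white cohort also had DEXA; the preliminary section gives fat mass results without naming the method.

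State that race is in the pooled models. Under Specific Aim 1, Interpretation, report the race-attenuation test under both (a) and (b), and base any claim that complement acts independently of obesity on (b) only. In Specific Aims, reconcile the triglyceride statement with the adjusted value of 0.009 (−0.027 to 0.046).

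The cost is wording and a second set of models; BMI, waist and DEXA fat are already planned for the new subjects. The C3 standard error in (b) rises by up to about 30%. If adiposity is partly a mediator, (b) estimates a direct effect, so (a) and (b) should be read together.
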